7.4.3 Outcome variables

Subjective rewarding value of cigarillo flavoring will be measured with the Cigarette Evaluation Scale (CES) adapted for cigarillo use. The CES is an 11 item Likert-format (1=not at all to 7=extremely) self-report instrument with established validity and reliability ($\alpha > .80$). We will focus on the satisfaction subscale. Primary Outcome measured at visit 1.

Relative reinforcing value of cigarillo flavoring will be measured with a validated choice paradigm, evaluating the preference for sweet flavored vs non-flavored cigarillos. RRVF will be defined by the breakpoint (highest trial completed across 10 trials to earn puffs for sweet flavored versus non-flavored cigarillos) Primary Outcome measured at visit 2.

Absolute reinforcing value of cigarillo flavoring is operationalized as the number of sweet flavored versus non- flavored cigarillo puffs consumed during the ad libitum smoking session. A research assistant will videotape, monitor, and count the number of cigarillo puffs taken during the 90- minute period. The primary comparison is the amount of consumption (puffs) of the sweet flavored versus non-flavored cigarillo. Primary Outcome measured at visit 3.

7.5 Analytic Plan

Prior to analyses, standard data cleaning, assumption evaluation, and imputation methodology will be applied. We conservatively assume that 85% of our participants will complete all study visits, and will recruit additional subjects (15%, 13) to replace those who fail to return. The baseline characteristics of subjects who drop out will be examined, with attention to whether there is an association between dropout and flavor preference. Female sex and race will be included in each model. We will also consider baseline variables potentially important to flavor preference (e.g., cigarette smoking status, menthol brand, cigarillo history, prior flavor preference, blunt use, depression, sensation-seeking, cigarillo flavor risk beliefs, and exposure to cigarillo flavor marketing) for inclusion in the multivariate models if bivariate associations with the outcome are $p \leq .20$. Outcomes will be analyzed using general linear models (GLM) with outcome family and links appropriate to each of the respective measures. Where measures are repeated, GLMs will be fitted with generalized estimating equations (GEE).

Aim 1 H1 will determine whether the subjective rewarding value of a sweet flavored cigarillo is greater than that of a non-flavored cigarillo among young adults. H1 will test whether participants report greater subjective rewarding value from a sweet flavored cigarillo than a non-flavored cigarillo. The outcome measure used for analysis is a continuous subjective rating of reward for sweet flavored and non-flavored cigarillos obtained at the first exposure (visit 1). The analysis will use a paired t-test (or GLM equivalent) to assess the effect of flavor. Female sex and race will be included in the model.

Aim 1 H2 will determine whether the relative reinforcing value of a sweet flavored cigarillo is greater than that of a non-flavored cigarillo among young adults. H2 will test whether participants “work harder” for sweet flavored cigarillo puffs than non-flavored cigarillo puffs (i.e., higher relative reinforcing value) as measured by a choice task. Participants will be given the choice to “work for” sweet flavored puffs at an increasing behavioral cost (more mouse clicks) or non-flavored puffs at a low fixed cost. The outcome variable used for this analysis is a breakpoint representing the highest level of work a participant will perform for a puff of a sweet flavored cigarillo. Flavor is inherent in the breakpoint outcome and will be assessed using a GLM.

Aim 1 H3 will determine whether the absolute reinforcing value of a sweet flavored cigarillo is greater than that of a non-flavored cigarillo among young adults. H3 will test whether participants take more puffs from a sweet flavored cigarillo versus a non-flavored cigarillo during the ad-libitum smoking session. The outcome measure is puff counts of sweet flavored and non- flavored cigarillos, and preference will be estimated as a rate-ratio using negative binomial mixed models.

CONFIDENTIAL

This material is the property of the University of Pennsylvania. Do not disclose or use except as authorized in writing by the study sponsor

Sample Size / Power. The proposed study is a within-subjects design. The sample size is driven by the test for H3. Because we have three experimental outcomes, we will Bonferroni correct our global alpha of 5% for three tests. Informed by the effect size of our prior study investigating e-cigarette flavoring (Cohen's d of 0.5) with a small within-subjects correlation (negative binomial model) of $r=0.13$. A sample of 86 yields 80% power to detect an effect size of 0.5, testing at alpha = 0.017.

8 Risks / Benefits

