5 CHARACTERISTICS OF THE STUDY POPULATION

5.1 *Target Population*

Participants will be 86 male and female young adults (ages 18-24 years old) who have used \geq 10 cigarillos in their lifetime.

We chose \geq 10 cigarillos/lifetime as a minimum criterion for participation to ensure that cigarillo exposure during the course of the study does not exceed lifetime exposure. As such, completely naïve young adults will not be exposed to cigarillos and regular cigarillo users with well-developed biases in favor of flavored cigarillos will not be included. We will measure cigarillo use history (flavor, non-flavored) and flavor preferences at baseline.

5.2 *Accrual*

We propose to recruit 100 young adults to ensure 86 participants with complete data at study end. Young adults will be recruited from the community through Internet-based advertisements (e.g., Craigslist, social media) and print advertisements including publications at 2-year and 4-year universities. Young adults who respond to the ads will be prescreened for inclusion and exclusion criteria over the telephone. In order to determine whether the ad respondents meet the inclusion criteria for lifetime cigarillo use, use of cigarillos and other tobacco products (e.g., large and little cigars) will be measured and differentiated through product description, and brand examples of the most popular brands of each product will be provided to aid accurate reporting. Research indicates that the inclusion of brand information increases self-reported cigar use. We will assess whether cigarillos and other cigar products are used as intended or modified for blunting. Cigar products modified for blunting will not count toward the inclusion cutoff for cigar exposure. The number of cigarillo blunts used in the past month and the brand characteristics (untipped, flavor) will be recorded at baseline.

Those meeting initial criteria will be screened at the beginning of Laboratory Visit 1 at the Bio-Behavioral Laboratory (BBL). After providing written informed consent, potential participants will provide a urine sample for a drug screen and a pregnancy test (females only) to determine final eligibility.

CONFIDENTIAL

This material is the property of the University of Pennsylvania. Do not disclose or use except as authorized in writing by the study sponsor

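### At the plan's own 85% completion rate, 99 recruits (implied by 7.5) or 100 (5.2) give about 84 or 85 completers, not the 86 that 5.2 promises

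*Combined protocol and SAP*

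**What the plan says.** Two sections of the combined protocol and SAP deal with accrual.

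- Section 7.5, Analytic Plan: "We conservatively assume that 85% of our participants will complete all study visits, and will recruit additional subjects (15%, 13". The sentence goes on to give the purpose of the extra subjects: "to replace those who fail to return". No total is printed; 86 plus 13 is 99.
- Section 5.2, Accrual: "We propose to recruit 100 young adults to ensure 86 participants with complete data at study end".

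The figure of 86 comes from the power statement at the end of 7.5: "A sample of 86 yields 80% power to detect an effect size of 0.5, testing at alpha = 0.017". The same paragraph says "The sample size is driven by the test for H3". H3 concerns puff counts in the ad-libitum session, described in 7.4.3 as "Primary Outcome measured at visit 3", so only participants who reach the last visit contribute to it.

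The number 86 also appears as the study size in the Study Summary (section 1), the last paragraph of 2.1, 4.1 and 5.1. Section 4.2 uses it as an upper limit on completers.

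**The concern.** Section 7.5 inflates the target by 15% when the stated loss is 15% of those recruited. These are different operations. The extra 13 subjects are exposed to the same loss as the first 86, so multiplying by 1.15 falls short of dividing by 0.85. Section 5.2 has a slightly larger figure, but it too falls short at 85% completion, although it is worded as a guarantee. The two sections also imply different totals.

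The number analysed for H3, the hypothesis that sets the sample size, would be expected to fall below the number at which power is quoted. A reader would also be told that 86 complete cases are assured when, on the plan's own rate, falling short is the more likely outcome.

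**Working it through.** **Inputs.** Target with complete data: 86 (5.2, 7.5). Completion: 85% (7.5). Extra subjects: 13 (7.5). Planned recruitment: 100 (5.2). For power: d = 0.5, r = 0.13, alpha = 0.017 (7.5).

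**Reproducing the plan's 13.** 0.15 × 86 = 12.9, rounded to 13, and 86 + 13 = 99. So 7.5 took 15% of the target.

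**Expected completers at 85%.**

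- 99 recruits: 0.85 × 86 + 0.85 × 13 = 73.1 + 11.05 = 84.15. The sum is the same whether the 13 enter at the start or later as replacements, provided that 13 is the limit.
- 100 recruits: 0.85 × 100 = 85.0.
- Needed for an expected 86: 86 / 0.85 = 101.2, so 102, which gives 0.85 × 102 = 86.7.

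**Completion rate at which the expected yield is 86.** 86/99 = 86.9%; 86/100 = 86.0%. Both exceed the 85% that 7.5 calls conservative.

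**Chance of at least 86 completers.** The number completing is taken as Binomial(N, p). Independence between participants is an assumption.

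| Recruited | p = 0.85 | p = 0.86 | p = 0.87 |
|---|---|---|---|
| 99 | 36% | 47% | 59% |
| 100 | 46% | 57% | 68% |
| 102 | 64% | 74% | 83% |

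The first column uses the plan's rate. The other two are assumed values that show how sensitive the result is.

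**Cost in power.** The planned H3 analysis is a negative binomial mixed model. Its power cannot be recomputed because no mean counts or dispersion are given. A two-sided paired t-test serves here only to gauge what losing one or two completers costs. It uses dz = d / √(2(1 − r)), so dz = 0.354 at r = 0 and 0.379 at r = 0.13, with the noncentral t distribution at alpha = 0.017.

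| Completers | r = 0 | r = 0.13 |
|---|---|---|
| 86 | 79.87% | 85.75% |
| 85 | 79.32% | 85.28% |
| 84 | 78.75% | 84.79% |

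Going from 86 to 85 costs 0.55 or 0.47 points. Going from 86 to 84 costs 1.12 or 0.96 points. Two-sidedness and the scaling of d to the raw standard deviation are assumptions, since 7.5 states neither.

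**The case against.** **Replacement may be open-ended.** Section 7.5 describes the extra subjects as replacements, so the plan might mean to recruit until 86 complete, with 13 as a forecast. This is possible, but 7.5 gives 13 and 5.2 gives 100, and neither says that recruitment continues past those numbers. A fixed 13 leaves the expected yield at 84.15. The objection is a good reason to state the replacement rule.

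**99 is not printed.** True: it is inferred from 86 + 13, and 100 may simply be 99 rounded up. The gap between 99 and 100 is therefore a small point. The shortfall at 85% remains with either figure.

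**85% is called conservative, and 4.2 is softer.** If completion is really 86% or 87%, 100 recruits reach 86 with probability 57% or 68%. Section 4.2 speaks only of up to 86 completers. Both points stand as reasons to treat the matter as minor. They do not justify the guarantee in 5.2, because 85% is the only completion rate the plan offers.

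**A stronger inference about power.** A reader who notices that the paired t-test gives 79.9% at r = 0 and 85.8% at r = 0.13 might infer that the printed correlation was ignored and that the 80% is an error. The documents do not support this. The H3 analysis is described as follows: "preference will be estimated as a rate-ratio using negative binomial mixed models". The correlation is also tied to that model: "with a small within-subjects correlation (negative binomial model". Other calculations that keep r = 0.13 come close to 80% at n = 86: a two-sided signed-rank calculation at its minimum relative efficiency of 0.864 gives 79.3%, and an unrounded d of 0.47, which would print as 0.5, gives 80.6% with the paired t-test. Neither is stated in the plan. They show only that the mismatch has more than one possible explanation.

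**Conclusion.** The accrual statement is wrong by a small amount. Section 7.5 multiplies by 1.15 where its own completion rate calls for division by 0.85. As a result, 99 recruits yield an expected 84.2 completers and 100 yield 85.0, while an expected 86 needs 102. The promise in 5.2 is not met at 85% completion: the chance of at least 86 is 46% with 100 recruits and 36% with 99.

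This rests on 85% as the completion rate, on 13 and 100 as fixed limits and, for the two probabilities only, on independent dropout. The consequence is one or two completers and about 0.5 to 1.1 percentage points of power on the paired-t approximation.

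It is a minor correction. It does not show that the study is underpowered, and the stated 80% is not shown to be wrong for the planned negative binomial model.

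**What to change.** Put one accrual figure in 5.2 and 7.5. For example: *We will recruit 100 young adults; at 85% completion we expect about 85 with complete data.* This would replace the guarantee of 86 in 5.2 and the 15% and 13 in 7.5. Quote power at 85 completers. Then align the other statements of 86 in the Study Summary, the last paragraph of 2.1, 4.1, 4.2 and 5.1, making clear in each whether the number is recruited, expected to complete, or analysed.

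Two alternatives are equally consistent:

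- Keep 86 as the expected yield and plan 102 recruits.
- If replacement is to continue until 86 complete, state that rule and the maximum to be recruited.

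As an optional clarification, 7.5 could name the method behind the 80%, its sidedness, how r enters, the scaling of d, and the mean counts and dispersion if a negative binomial calculation was used.

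The cost is wording in these sections and a power figure restated at the chosen number. Keeping 100 changes nothing in recruitment; moving to 102 adds two participants.

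### H2 is a one-sample test of the mean breakpoint, so the rule that sex and race enter every model can move the test to one subgroup or understate its standard error

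*Combined protocol and SAP*

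**What the plan says.** Section 7.4.3 sets the scale: "RRVF will be defined by the breakpoint (highest trial completed across 10 trials to earn puffs for sweet flavored versus non-flavored cigarillos"). For the H2 analysis, Section 7.5 adds: "The outcome variable used for this analysis is a breakpoint representing the highest level of work a participant will perform for a puff of a" (the sentence ends by naming the flavored product). On how the flavor effect is obtained, it says only: "Flavor is inherent in the breakpoint outcome and will be assessed using a GLM".

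The covariate rule in Section 7.5 is general: "Female sex and race will be included in each model". The same section screens further baseline variables into the multivariate models when their bivariate p-value is .20 or less. Section 7.4.2 goes further for some of these, stating without a screen that cigarillo use history (number and flavor preference) and depression symptoms go into the statistical models.

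On the model itself: "Outcomes will be analyzed using general linear models (GLM) with outcome family and links appropriate to each of the respective measures". The H2 family and link are not named. The plan also does not give the coding or centring of covariates, any marginal-mean step, the variance estimator, or the breakpoint value that would represent no preference. On multiplicity: "we will Bonferroni correct our global alpha of 5% for three tests".

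**The concern.** In a model that contains a flavor contrast, baseline covariates are routine, because the flavor coefficient keeps its meaning when sex and race are added. H2 has no such coefficient. With one record per person and flavor built into the outcome, the result can only be the level of the breakpoint, that is, an intercept or a mean. Adding covariates then changes either what the intercept describes or how its standard error is computed. Neither change gives a more precise answer to the question asked, which is about young adults as a whole.

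H2 is one of three primary tests, each at 0.05/3. If coding and variance are left to software defaults, the primary conclusion may concern one reference subgroup, or may rest on an interval that is too narrow. Naming a reference value for the breakpoint is necessary but does not settle this. It would still be unclear whose mean is compared with that value, and with what standard error.

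**Working it through.** **Inputs from the documents.** One breakpoint per person on a 10-trial scale; sex and race in every model; other covariates by rule or by screen; 86 participants with complete data; alpha 0.05/3 = 0.0167, printed as 0.017. The plan states no standard error, power or null value for H2, so there is no H2 figure to reproduce. The power statement for 86 participants is tied to H3 and is not used here.

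**Assumptions.** Two-sided testing (sidedness is not stated), a linear model for the breakpoint, and R² from 0 to 0.30 for the covariates. Sex is split 50/50 and race 50/35/15, independently of sex. None of these is in the documents.

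**1. Reference coding, covariates not centred.** The intercept is the mean for the reference sex and race, with every continuous covariate at zero. Relative to residual variance/n, its variance is

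1 + Σ(covariate means, scaled by their inverse covariance).

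- Sex: 0.5²/(0.5×0.5) = 1.
- Race dummies: (1−p_ref)/p_ref = 0.5/0.5 = 1.
- Total: 1 + 1 + 1 = 3, so the standard error is multiplied by √3 = 1.73.
- With a reference race share of 40% the total is 1 + 1 + 1.5 = 3.5; with 60% it is 1 + 1 + 0.67 = 2.67.

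Relative to the variance of the plain mean, these factors are multiplied by (1−R²).

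The target also moves. Suppose the overall mean equals the reference value but the reference subgroup lies δ SD away. The shift in the test statistic is about δ√86/1.73 (ignoring the small change in residual SD):

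- δ = 0.2: 1.07, giving rejection in about 9% of trials.
- δ = 0.3: 1.61, giving rejection in about 22%.

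A simulation (n = 86, 8,000 runs, two equal race groups) split R² = 0.10 equally between sex and race. That puts the reference cell 2×√0.05 = 0.45 SD from the mean, and the intercept test rejected in 53% of runs. The size depends entirely on how far the subgroup lies from the whole.

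Continuous or ordered covariates add to this. If lifetime cigarillo number entered uncentred, the intercept would describe someone with none, whom the 10-cigarillo entry criterion excludes.

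**2. Mean-centred covariates.** The fitted intercept is now exactly the sample mean. Its sampling variance as an estimate of the population mean is total variance/n. The model reports residual variance/n, so

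model SE / correct SE = √(1−R²), and actual size = 2·P(Z > 2.394·√(1−R²)).

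| Assumed R² | SE ratio | Actual size (nominal 1.67%) |
|---|---|---|
| 0 | 1.00 | 1.67% |
| 0.05 | 0.975 | 2.0% |
| 0.10 | 0.949 | 2.3% |
| 0.20 | 0.894 | 3.2% |
| 0.30 | 0.837 | 4.5% |

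Simulation at the printed 0.017 agrees. With sex and race only, sizes were 1.8%, 2.2%, 3.5% and 4.3% at R² of 0, 0.10, 0.20 and 0.30. With nine further candidates screened at p ≤ .20, they were 2.2%, 2.5%, 3.7% and 4.8%.

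**3. Robust errors.** The sandwich variance of the centred intercept is Σe²/n², which still uses residuals only. Simulated sizes were the same as with model-based errors in every setting.

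**4. Unadjusted mean with SD/√n.** Simulated size was 1.6% to 1.9% across all settings, in line with the nominal 1.7%.

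**The case against.** The strongest reply is that the plan is silent on coding and variance rather than wrong about them. An analyst could compute a standardized mean with a variance that counts covariate sampling, and nothing in Section 7.5 forbids it. That stands: this is an under-specification, and the two outcomes worked above are neither certain nor exhaustive. What is stated, however, is that sex and race go in each model, with no exemption for H2 and no step that recovers the overall mean. Effect coding is also open, but its intercept weights the cells equally, so it is not the sample mean either.

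Second, the background section says the study will examine whether the indices remain significant when other factors are controlled, which suggests an uncontrolled result comes first. This softens the point for the screened covariates. It does not override the sex-and-race rule.

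Third, the centred model's standard error is correct if inference is conditional on the covariate values that happened to be sampled. That is true, but the objective is framed for young adults, not for this sample's mix.

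Fourth, R² is unknown and may be small. A sample R² of 0.10 at n = 86 adjusts to about 0.07 with 3 terms and 0.01 with 8. This stands, and it limits the size of the second problem.

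Fifth, the missing reference value is the larger gap. Also true, and the two should be fixed together.

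**Conclusion.** The point holds as a gap in the primary H2 analysis. The result is a one-sample mean, and the stated covariate rule cannot sharpen it. Under default coding the rule moves the test to a reference subgroup whose mean has about 3 times the variance (2.67 to 3.5 over the race splits tried, before the 1−R² factor). Under centring it raises the size from 1.67% to between 2.0% and 4.5% for R² of 0.05 to 0.30, and hardly at all if R² is near 0. These figures rest on an assumed covariate mix, R², linear model and two-sided test.

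Four stronger readings are tempting but not supported:

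- **That missing robust errors are the cause.** The plan reserves GEE for repeated measures, but robust errors would change neither the subgroup described by the intercept nor the centred standard error.
- **That a binomial or Poisson variance would misstate the error.** The plan requires a family appropriate to each measure, so a clearly ill-fitting one would not comply.
- **That H1 is affected too.** H1 names a paired t-test or GLM equivalent on repeated ratings. With flavor as a within-person term, sex and race main effects do not turn it into a subgroup mean.
- **That H2 falls from a planned 80% power.** The plan states power for H3 only.

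**What to change.** In Section 7.5, exempt the primary H2 test from the rule on covariates in each model, and align Section 7.4.2 with that. State the reference value for the breakpoint. Define the primary test as the unadjusted mean breakpoint over all participants with outcome data against that value, with a standard error from the observed between-person SD or a bootstrap that resamples participants. Report covariate-adjusted models as secondary, giving a standardized mean with a bootstrap that resamples participants.

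The cost is SAP wording only; no extra participants or data are needed. The downside is that the apparent precision gain from adjustment is lost, but for the population mean that gain was not real.
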